The study will be unblinded to the Sponsor (Romark) and Medical Monitor after all subjects have completed 12 weeks of treatment and complete data is collected through that time point for

analysis of safety and the primary efficacy parameter (mean change in qHBsAg at Week 12). The investigators, subjects and clinical monitors will remain blinded throughout the study.

Rationale for study design: *In vitro* data suggest that NTZ may be effective in inducing loss of HBsAg in patients with CHB. Cell culture studies have shown that combinations of NTZ with the NrtIs, lamivudine, adefovir dipivoxil, TDF and ETV are synergistic in inhibiting HBV replication. The NrtIs are poorly effective in producing HBsAg loss or seroconversion, and therefore, patients must remain on chronic therapy in order to maintain suppression of HBV DNA. With this background, this study is designed to evaluate whether the combination of NTZ plus TDF, TAF or ETV is superior to TDF, TAF or ETV alone in reducing quantitative serum HBsAg. TDF, TAF or ETV were selected for use in this study because they are widely used for treating CHB and because of their potency in reducing serum HBV DNA and superior resistance profiles. This study is a Phase 2 study, and therefore, the number of subjects per treatment arm is low. This study is designed to provide data, including dose-range-finding data, to determine whether NTZ reduces qHBsAg and to guide future development of NTZ in treating CHB infection.

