The duration of treatment to the primary endpoint (12 weeks) is designed to provide a relatively quick determination regarding whether NTZ induces a meaningful reduction of qHBsAg. Subjects will be allowed to continue treatment beyond 12 weeks if they are showing progressive declines in qHBsAg or if they experience HBsAg loss. The stopping rules require discontinuation of the investigational medication in the event that a subject fails to achieve any decline in qHBsAg from Baseline to Week 12, at least a 0.5 log₁₀ decline from Baseline to Week 24, at least a 1 log₁₀ decline from Baseline to Week 48, at least a 2 log₁₀ decline from Baseline to Week 72 or HBsAg loss at Week 96. The generally accepted stopping rule for peginterferon is less than a 1 log₁₀ decline of HBsAg at Week 12. The stopping rules for this study were selected because (1) there is insufficient information regarding the potential qHBsAg response patterns to NTZ and (2) use of NTZ for durations longer than 12 weeks has not been associated with significant safety issues. Subjects achieving HBsAg loss and HBV DNA suppression will continue treatment with the investigational medication and NrtI until they have maintained HBsAg loss and HBV DNA suppression for 24 weeks on treatment (consolidating therapy). The extended duration of treatment for subjects showing response to treatment is designed to allow subjects to continue treatment if they are experiencing benefit with respect to

qHBsAg. It also allows for collection of data regarding the duration of treatment for future clinical development.

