7.1. Inclusion Criteria

1. Age at least 21 years.
2. CHB virus infection (serum HBsAg-positive for at least 6 months or serum HBsAg positive and negative immunoglobulin M (IgM) antibodies to HBV core antigen (IgM anti-HBc).
3. HBeAg negative.
4. Virologically suppressed (HBV DNA less than the lower limit of quantitation) for at least 12 months on TDF, TAF or ETV therapy.
5. Quantitative HBsAg greater than 100 IU/mL.
6. ALT below 1.5 times the upper limit of normal.
7. Able to comply with the study requirements.

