8. RANDOMIZATION

An independent third party will prepare a master randomization list and maintain the masking of the study. Subjects who qualify for the study will be assigned to treatment using centralized randomization procedures stratified by qHBsAg (less than 3, 3 to 4, greater than 4 \log_{10} IU/mL) and NrtI therapy (TDF, TAF or ETV). The treatment numbers will appear on the medication kits containing the masked study medication. The randomization list will be masked to study participants including Sponsor, Investigators, study monitors, subjects and laboratory personnel. Unmasking for any individual subject will occur only if necessitated by emergency and knowledge of the medication being taken will influence the medical management of the subject. Furthermore, if the event warrants submission of a safety report to regulatory authorities, then the subject's treatment assignment will be unmasked for completion of the report. If a subject is lost to follow up or discontinues the study prior to the assessment at week 12, an additional subject may be enrolled in the same treatment group.

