11. STATISTICAL CONSIDERATIONS

11.1. Sample Size Calculation

The study is designed to evaluate the safety and efficacy of three different NTZ treatment regimens compared to placebo as add-on therapy to TDF, TAF or ETV in reducing quantitative HBsAg (in order to select a dose for future clinical trials).

A student's t-test with a 0.05 two-sided significance level will have 90% power to detect the difference between a mean change of 0.5 log10 for one treatment group and no change for the other treatment group when sigma (common standard deviation) is 0.33 and the sample size in each group is 10. A sample size of 12 per group was selected in order to allow for the possibility of up to 2 non-evaluable subjects per group (due to drop-out, etc.).

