11.2. Efficacy Variables

Primary Efficacy Parameter: The mean change in qHBsAg from Baseline to Week 12.

Secondary Efficacy Parameters:

- i. Sustained HBsAg loss with suppression of HBV DNA for 24 weeks after the end of treatment.
- ii. Change in qHBsAg from Baseline to different time points on treatment.
- iii. HBsAg loss.
- iv. HBsAg seroconversion.
- v. HBV DNA suppression.
- vi. Change from Baseline in Fibrosis 4 (FIB-4) score.
- vii. Change from Baseline in FibroScan® score.

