11.4.1. Efficacy Analyses

The study will be unblinded to the Sponsor (Romark) and Medical Monitor for analysis of efficacy and safety data after all subjects have completed 12 weeks of treatment and complete data is collected through that time point. The investigators, subjects and monitors will remain blinded throughout the study.

Efficacy analyses will be based on a population consisting of all subjects randomly assigned to the study (“intent-to-treat” population). In the event that there are significant numbers of subjects who fail to complete the study, violate the protocol, or are noncompliant with the study medication, efficacy analyses will also be conducted for a population excluding these subjects (“per protocol population”).

Primary efficacy analyses will be conducted as follows: For each NTZ treatment group, the mean change in qHBsAg from Baseline to Week 12 will be compared to that of the placebo treatment group.

Secondary efficacy analyses will be conducted as follows:

- For each of the three NTZ groups, the proportion of subjects with sustained suppression of HBV DNA and HBsAg loss at 24 weeks after the end of treatment will be compared to the proportion for the placebo treatments group.
- For each NTZ dose group and for each study time point, the change in qHBsAg from Baseline will be compared to the change in qHBsAg for the placebo treatment group.
- For each of the three NTZ groups and for each study time point, the proportion of subjects with HBsAg loss will be compared to the proportion for the placebo treatments group.
- For each of the three NTZ groups and for each study time point, the proportion of subjects with HBsAg seroconversion will be compared to the proportion for the placebo treatments group.
- For each of the three NTZ groups and for each study time point, the proportion of subjects with quantifiable HBV DNA at Baseline who experienced HBV DNA suppression will be compared to the proportion for the placebo treatments group.
- For each NTZ dose group and for each study time point, the mean change in Fibrosis 4 (FIB-4) score from Baseline will be compared to the change for the placebo treatment group.
- For each NTZ dose group, the mean change in FibroScan® score from Baseline to end of treatment and to end of off-treatment follow-up will be compared to the change for the placebo treatment group.

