Means will be compared by two-sided student’s t tests, $\alpha = 0.05$. Nonparametric data will be analyzed using the Wilcoxon rank sum (Mann-Whitney) test. Proportions will be compared using a two-sided Fisher’s Exact test, $\alpha = 0.05$. In the setting of an early Phase 2 study, no adjustments for multiplicity are planned.

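### The primary t-tests leave out the randomisation factors; a pre-specified four-arm ANCOVA with variance-robust intervals would be more precise if baseline qHBsAg predicts the change

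*Combined protocol and SAP*

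**What the plan says.** - Section 8: subjects are "assigned to treatment using centralized randomization procedures stratified by qHBsAg" (three bands, cut at 3 and 4 log10 IU/mL) and by NrtI (TDF, TAF or ETV). That makes nine strata for 48 subjects.
- Section 11.2 gives the primary parameter: "The mean change in qHBsAg from Baseline to Week 12". Baseline is therefore subtracted from the outcome.
- Section 11.4.1 gives the primary comparison: "For each NTZ treatment group, the mean change in qHBsAg from Baseline to Week 12 will be compared to that of the placebo treatment group". The method is "Means will be compared by two-sided student’s t tests" at a 0.05 level. The Wilcoxon test is named for nonparametric data. No covariate, stratified test or model appears.
- Section 11.1 sizes the trial on the same unadjusted test, for 90% power to detect 0.5 log10 "when sigma (common standard deviation) is 0.33 and the sample size in each group is 10". Twelve per arm are randomised to allow for dropout.
- Section 11.4 says that its description is brief and leaves detail to a Statistical Analysis Plan. No separate SAP text is in the material supplied.
- Section 6 sets the timing: "The study will be unblinded to the Sponsor (Romark) and Medical Monitor after all subjects have completed 12 weeks of treatment".

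**The concern.** Two factors are considered important enough to control at randomisation, and neither enters the analysis. Subtracting baseline is not the same as adjusting for it, because the size of the change may still depend on the starting level. NrtI does not enter at all.

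If baseline predicts the change, stratification makes the arms more alike than the t-test's standard error assumes. The test then becomes conservative and its interval wider than necessary. The trial is meant to choose a dose from three dose-placebo differences with 10 to 12 subjects per arm, so interval width matters. Both factors are already recorded, so any variance they explain could be removed without new data.

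**Working it through.** **Inputs from the documents.** Effect 0.5 log10, SD 0.33, 10 evaluable per arm, two-sided 0.05 (Section 11.1); four equal arms, 48 subjects (Synopsis); strata (Section 8); "Quantitative HBsAg greater than 100 IU/mL", that is, above 2 log10 (Section 7.1).

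**Assumptions, not in the documents.** Baseline log10 qHBsAg normal with mean 3.3 and SD 0.7, truncated above 2; TDF/TAF/ETV 40/20/40%; permuted blocks of 4 in each stratum; no NrtI effect; correlation r between baseline and change of 0, 0.3 or 0.5. Section 6 itself says that "there is insufficient information regarding the potential qHBsAg response patterns to NTZ", so r can only be a range.

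**1. The plan's own figure.** Noncentrality = 0.5 / (0.33 × √(2/10)) = 0.5 / 0.1476 = 3.39 on 18 df. Power is 89.3%, which agrees with the stated 90%.

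**2. What adjustment can change.** Residual SD = 0.33 × √(1 − r²), which is 0.330 / 0.315 / 0.286 at r = 0 / 0.3 / 0.5. Error df are 18 for the t-test, 40 − 4 = 36 for an unadjusted four-arm model, and 40 − 4 − 3 = 33 for the four-arm ANCOVA (baseline takes 1, NrtI takes 2).

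**3. Power by simulation.** 48 subjects were randomised in strata and cut at random to 10 per arm (37,686 usable trials, simulation error about 0.15 points):

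| Analysis | r = 0 | r = 0.3 | r = 0.5 |
|---|---|---|---|
| Planned t-test | 89.0% | 90.0% | 90.2% |
| Unadjusted four-arm model | 90.7% | 91.6% | 92.0% |
| Four-arm ANCOVA, pooled variance | 89.7% | 92.6% | 96.2% |
| Separate two-arm ANCOVAs | 86.0% | 89.5% | 94.0% |

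At r = 0.3 the ANCOVA gains 92.6 − 90.0 = 2.6 points over the planned test. Of these, 91.6 − 90.0 = 1.6 come from pooling and 92.6 − 91.6 = 1.0 from adjustment. At r = 0 adjustment costs 90.7 − 89.7 = 1.0 point against the unadjusted four-arm model, yet the ANCOVA is still 89.7 − 89.0 = 0.7 above the planned test.

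Break-even for adjustment alone (unadjusted four-arm against ANCOVA): 91.2 / 90.7% at r = 0.15, 91.3 / 91.2% at 0.20, 91.3 / 91.8% at 0.25. So it lies near r = 0.2.

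**4. If stratified balance is not achieved.** Averaging over chance covariate layouts at 10 per arm, the ANCOVA has 88.1% at r = 0 against 89.3%, a cost of 1.2 points. It has 90.9% at r = 0.3 and 95.2% at r = 0.5.

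**5. Precision and error rate.** Mean 95% CI half-width is 0.306 to 0.308 log10 for the t-test and 0.303 / 0.289 / 0.262 for the ANCOVA. The reduction at r = 0.5 is (0.307 − 0.262) / 0.307, about 15%. Type I error at 12 per arm is 5.0 / 4.3 / 3.7% for the t-test and 5.0 / 4.8 / 5.2% for the ANCOVA.

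**6. Unequal arm SDs.** Assumed SDs are 0.2 (placebo) and 0.2 / 0.33 / 0.5 (low, middle, high dose), with r = 0 and 10 per arm:

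| Analysis | Null rejection, low / middle / high | Power at a true 0.3 log10 |
|---|---|---|
| Planned t-test | 5.0 / 5.4 / 5.7% | 89 / 65 / 40% |
| Welch test | 4.9 / 5.1 / 5.0% | not tabulated |
| Four-arm ANCOVA, pooled variance | 0.4 / 2.3 / 8.9% | 49 / 50 / 50% |

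**7. Robust standard errors.** A baseline-only four-arm model with HC3 errors and 17 df, under equal SDs, falls about 3 to 4 points below the planned t-test at r = 0. It is near break-even at r = 0.3 and about 4 points above at r = 0.5.

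**The case against.** The strongest objection concerns the remedy. An ANCOVA with one pooled variance could harm the comparisons it is meant to sharpen. Under the unequal SDs above, the low dose loses 89 − 49 = 40 points of power, while the high dose gains 10 points through an inflated error rate. In a dose-finding trial that favours the highest dose. The common SD in Section 11.1 does not answer this, because that section describes one two-group test and not four arms. This objection stands, and it is why the variance safeguard belongs in the primary analysis and not only in a sensitivity analysis.

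It is also fair that no r is documented, that the planned test is a defensible choice for a small Phase 2 trial, that NrtI adjustment has no demonstrated benefit, and that Section 8 allows replacement, so 12 per arm is plausible. At 12 per arm the t-test already has 94.4% power and there is less to gain.

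The deferral to a SAP leaves open that covariates are specified there. It does not alter the fact that the method named in Section 11.4.1 has none.

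A reader might also infer that the four-arm ANCOVA costs about 1 point against the planned test when neither factor matters. Under stratified balance that cost is only against an unadjusted four-arm model, which the plan never proposes. Against the planned test it arises only if balance fails.

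**Conclusion.** The point holds as a modest, optional gain in precision. Under stratified balance and equal SDs, a four-arm ANCOVA loses nothing against the planned t-test at r = 0, and gains about 3 points at r = 0.3 and about 6 at r = 0.5. About 1.5 points of this come from pooling. With robust errors the trade is less favourable: a loss at r = 0, near break-even at r = 0.3, and a gain only for larger r. All of this rests on the assumed r, baseline distribution, NrtI mix and block size.

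A reader might infer that ignoring the stratification factors makes the primary test invalid or leaves the trial underpowered. The documents do not support either reading. The error rate stays at or below 5% under equal SDs, and the stated 90% power reproduces without any adjustment.

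**What to change.** Before the sponsor is unblinded at Week 12, pre-specify in Section 11.4.1 and the SAP:

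- One four-arm ANCOVA of change in log10 qHBsAg, with continuous baseline log10 qHBsAg and NrtI as main effects, not the nine strata. Do not use separate two-arm ANCOVAs.
- A rule for sparse NrtI levels. For example, merge TDF and TAF if either has fewer than 4 analysed subjects, and leave NrtI out if ETV does. If the rarest NrtI has an assumed 20, 10 or 5% share, it has fewer than 4 of 40 subjects in 3.5, 45 or 87% of trials.
- Each dose-minus-placebo difference with its 95% CI.
- Primary tests and intervals based on arm-specific variances or small-sample robust standard errors such as HC3, or a stated criterion under which these replace the pooled ones if arm SDs clearly differ.
- The planned t-test, the Welch test and the Wilcoxon test as sensitivity analyses, with any disagreement reported.

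If the SAP already adjusts, align Section 11.4.1 with it.

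The cost is wording, with no new data. The downsides to state are up to 3 degrees of freedom, the distortion across doses if a pooled variance is used and arm SDs differ, and the loss of power at r = 0 if robust errors are used.

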11.4.2. Safety Analyses

All randomized subjects who receive the study medication will be assessed for drug safety. Safety analyses will be done descriptively.

12. INVESTIGATIONAL PRODUCTS

12.1. Identity of Investigational Products

NTZ 300 mg extended release tablets manufactured for Romark Laboratories, L.C. by Xcelience Inc., Tampa, Florida. Each tablet is a yellow, round, convex, film-coated, bi-layer tablet for oral administration, each tablet contains 300 mg of NTZ and the inactive ingredients.

The study medications will be provided by the study sponsor.

12.2. Packaging and Labeling

All study medication will be packaged and labeled by the study sponsor and its contractors. NTZ and placebo tablets will be packaged in white 30cc HDPE bottles, each containing 30 tablets. The bottles will be stored at room temperature. Do not store above 25°C and protect from moisture. The box and bottles will bear a label with the following information:

External Box Label

		Investigator Name
180 Tablets	RM08-2001	Treatment #
Lot#	Nitazoxanide/Placebo 300 mg Tablets	
EXP Date	Take one tablet from bottle A, B, and C by mouth each morning with food, and take one tablet from bottle D, E, and F by mouth each evening with food.	
	“For clinical trial use only”	
	Do not store above 25°C. Protect from moisture.	
	Study Sponsor: The Romark Institute for Medical Research	

Individual Bottle Label (AM Doses)

30 Tablets	RM08-2001	Treatment #
Lot#	Nitazoxanide/Placebo 300 mg Tablets	Bottle # (A-C)
	Take one tablet by mouth each morning with food.	
	“For clinical trial use only”	
	Do not store above 25°C. Protect from moisture.	
	Study Sponsor: The Romark Institute for Medical Research	

Individual Bottle Label (PM Doses)

30 Tablets	RM08-2001	Treatment #
Lot#	Nitazoxanide/Placebo 300 mg Tablets	Bottle # (D-F)
Take one tablet by mouth each evening with food.		
“For clinical trial use only”		
Do not store above 25°C. Protect from moisture.		
Study Sponsor: The Romark Institute for Medical Research		

Subjects will be provided with an information card containing the name, address, and telephone number of the best contact if they have questions.

12.3. Drug Accountability

Medication supplies will be dispensed at Baseline (Day 1) and every 4 to 12 weeks during the treatment period, depending on the visit schedule. Subjects will be asked to return any unused supplies at each visit.

The investigator is required to maintain adequate records of the disposition of all study drug, including dates, quantity and use by subject. Unused supplies must be returned to the Sponsor or destroyed in accordance with institutional procedures in effect at the study site.

12.4. Subject Compliance and Disallowed Medications

Subject compliance with the protocol will be checked by the Investigator and recorded in the CRF at each visit.

Subjects will be considered non-compliant if they have missed more than 20% of the doses of the study medication or if they take any antiviral drug active against HBV other than the investigational medication, TDF, TAF and ETV.

During the active treatment course of the study, concomitant use of medications considered major CYP2C8 substrates ([Section 23.1](#)) are prohibited. Subjects are also prohibited from taking any other investigational medication during the study.

13. ADVERSE EVENTS

The term “adverse event” is defined for purposes of this study as any unwanted physical, psychological or behavioral change experienced by a subject during the course of the study and after taking the first dose of study medication regardless of its severity or relation to the study. Adverse events may include symptoms, signs, unexpected worsening of pre-existing conditions, clinically significant changes in laboratory values, diseases and syndromes, and significant and unexpected failures of pharmacological action of other medications. Symptoms of CHB will not be reported as adverse events.

Adverse events will be recorded on the appropriate EDC forms throughout the study, and the severity of each adverse event will be graded on a four-point scale: mild, moderate, severe, or life-threatening (See [Section 23.3](#)). The duration of the adverse event and relationship to the study drug will also be recorded. All adverse events must be followed until their resolution or stabilization even beyond the planned study period.

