4.2.2. Clinical Experience with NTZ

4.2.2.1. Overall Clinical Experience

NTZ has been marketed for diarrheal disease caused by *Giardia* or *Cryptosporidium* in the United States since 2003. In Latin America, India, Bangladesh and Egypt the drug is marketed as a broad-spectrum antiparasitic agent. It is estimated that more than 300 million patients have been exposed to NTZ worldwide with the usual adult dose being 500 mg twice daily for three days. No significant drug-related AEs have been reported in post-marketing experience.

Over 6,000 subjects have been treated with NTZ in clinical trials, including 1,760 subjects 12 years of age and older who have been exposed to the NTZ 300 mg extended release tablets (as monotherapy, $n = 1,272$, or in combination with oseltamivir, $n = 488$). Of the 1,760 subjects, 1,374 were given a dose of 600 mg twice daily for 5 days. The most commonly (at least 2% of treated subjects) reported adverse events (AEs) regardless of causality assessment were: diarrhea (6.4%), chromaturia (4.7%), headache (3.5%), nausea (3.1%), abdominal pain/abdominal pain upper (3%), bronchitis (2.7%), and vomiting (2.3%). In the placebo-controlled trials, the rates of occurrence of AEs did not differ significantly from those of placebo except for chromaturia (4.7% vs 0.2%). Less than 1% of subjects discontinued therapy because of AEs.

Other clinical studies of NTZ immediate-release tablets, oral suspension, or other formulations have been conducted in more than 4,250 subjects. The dose was typically 500 mg to 1500 mg twice daily for adults and adolescents at least 12 years of age or 7.5 mg/kg/day for children under 12 years of age, and the duration of treatment was typically 3 to 14 days.

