The product has been studied for longer durations in subjects with acquired immune deficiency syndrome (AIDS) and cryptosporidiosis, and in subjects with chronic hepatitis C. A total of 660 subjects enrolled in these long-term studies received NTZ for more than 1 month (maximum of 1,528 days), of which 411 were treated for greater than 3 months, mostly at a dose range of 500 mg to 1350 mg twice daily. In 315 subjects with chronic hepatitis C, NTZ was administered at doses ranging from 500 mg to 1350 mg twice daily with food for up to 52 weeks. The AEs associated with long-term use of NTZ were primarily related to the gastrointestinal (GI) tract with mild to moderate and transient abdominal pain, diarrhea, headache and nausea being the most common AEs reported. Mild and transient yellow discoloration of the urine and sclera

have also been reported, particularly in subjects receiving doses of at least 1,000 mg BID for extended durations.

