 - Feeling very weak or tired.
 - Unusual (not normal) muscle pain.
 - Trouble breathing.
 - Stomach pain or nausea and vomiting.
 - Feeling cold, especially in your arms and legs.
 - Feeling dizzy or light-headed.
 - Fast or irregular heartbeat.
 - Yellowing of eyes or sclera.
 - Brown or dark urine.
 - Confusion.
 - Tightness in your throat or chest, rash (especially hives) or itchiness.

- Loss of appetite for several days or longer.
- Bowel movements (stools) turn light in color.

11. Randomization (see [Section 8](#)).

At the Baseline visit, subjects will be randomly assigned to one of the following treatment groups:

Group 1: PLACEBO - Subjects will receive three placebo tablets twice daily with food in addition to continuing TDF, TAF or ETV therapy.

Group 2: 600 mg NTZ QD - Subjects will receive two NTZ 300 mg extended release tablets and one placebo tablet in the morning and three placebo tablets in the evening with food in addition to continuing TDF, TAF or ETV therapy.

Group 3: 600 mg NTZ BID - Subjects will receive two NTZ 300 mg extended release tablets and one placebo tablet twice daily with food in addition to continuing TDF, TAF or ETV therapy.

Group 4: 900 mg NTZ BID - Subjects will receive three NTZ 300 mg extended release tablets twice daily with food in addition to continuing TDF, TAF or ETV therapy.

Subjects will be given a 4-week supply of medication and instructions on administration of the study medication. The NTZ and placebo tablets (yellow) must be administered with food. TDF, TAF or ETV tablets should be administered daily at the same time each day. The first dose of study medication should be taken in the clinic under the observation of the investigator.

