9.6. Study Medication Discontinuation and Withdrawal Criteria

Treatment with the investigational medication (NTZ/placebo) will be discontinued for individual subjects for the following reasons:

1. Subject withdraws consent.
2. A subject must discontinue study medication for the following medical or administrative reasons [reasons for discontinuing must be recorded in the case report form (CRF)]:
 - Violation of eligibility criteria.
 - Material deviation from the treatment plan specified in the protocol.
 - Progression of the disease which in the opinion of the investigator precludes further participation.
 - Women who become pregnant.
3. An adverse event deemed sufficiently severe to require study discontinuation. These include:
 - Grade 2 or higher rash at least possibly related to study drug.
 - Grade 3 or 4 acute systemic allergic reaction.
 - Grade 2 serum creatinine considered at least possibly related to the study drug by the investigator, or Grade 3 or 4 proteinuria on urinalysis, confirmed by retesting.
 - Grade 2 vomiting that persists despite anti-emetics, or Grade 3 or higher vomiting.
 - Grade 3 or higher diarrhea at least possibly related to study drug.

- Treatment-emergent elevation of ALT greater than 2x baseline, in combination with either bilirubin greater than 2x the upper limit of normal (ULN) or INR greater than 1.5x ULN or serum albumin less than the lower limit of normal (LLN), confirmed by retesting.
- Any Grade 4 AE or confirmed abnormality (except for AST/ALT elevations) considered at least possibly related to the study drug.
- Clinical signs of hepatic decompensation.
- QTcF prolongation (QTcF greater than 500 msec, or increase from baseline greater than 60 msec) at any time point, confirmed by repeat ECG.

4. Subject is:

- HBsAg positive with no decline in qHBsAg from Baseline at Week 12.
- HBsAg positive with less than a $0.5 \log_{10}$ decline in qHBsAg from Baseline at Week 24.
- HBsAg positive with less than a $1 \log_{10}$ decline in qHBsAg from Baseline at Week 48.
- HBsAg positive with less than a $2 \log_{10}$ decline in qHBsAg from Baseline at Week 72.
- HBsAg positive at Week 96.

5. HBsAg loss with HBV DNA suppression maintained on treatment for 24 weeks (consolidating therapy).

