13.2. Clinical Adverse Events

At the time of each return visit, the subject will be questioned regarding the occurrence and nature of any adverse events. All events must be recorded in the subjects' medical records and in the EDC system. Any subject affected will be examined by the Investigator as deemed necessary to ascertain the course of the event and any residual effects.

All moderate and severe adverse events will be reviewed by the Principal Investigator who will determine using his/her best clinical judgment whether they warrant the subject to be discontinued from the study. The Sponsor will be notified immediately if a subject is discontinued from the study. For all adverse events that require the subject to be discontinued from the study, relevant clinical assessments and laboratory tests will be repeated as clinically indicated until final resolution or stabilization of the event(s).

All subjects will be instructed to contact the Investigator, Investigator's assistants, or clinical personnel should the subject have any serious adverse experiences. Serious adverse events,

including death regardless of the cause, must be reported to the Sponsor immediately (within 24 hours of the initial report).

A serious event requiring immediate notification by telephone is an event that:

- results in death
- is life threatening
- requires inpatient hospitalization or prolongation of an existing hospitalization
- is a persistent or significant disability/incapacity
- is a congenital anomaly/birth defect
- an important medical event that may not result in death, be life-threatening, or require hospitalization but, based upon appropriate medical judgment, may jeopardize the subject and may require medical or surgical intervention to prevent one of the outcomes listed above.

An overdose is defined as any intentional or unintentional consumption of the drug by any route that exceeds the highest dose stated in the Investigator's Brochure, approved product labeling (for TDF, TAF or ETV) or in an investigational protocol, whichever dose is larger. Overdoses without an associated adverse event should be recorded, but not reported as an adverse event.

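### Section 13 excludes undefined symptoms of chronic hepatitis B from adverse event reporting, against its own definition, and this can lower the reported rates of events that resemble known nitazoxanide effects

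*Combined protocol and SAP*

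**What the plan says.** The first paragraph of Section 13 counts as an adverse event any unwanted change that occurs "after taking the first dose of study medication regardless of its severity or relation to the study". Its examples include "unexpected worsening of pre-existing conditions, clinically significant changes in laboratory values". The paragraph then closes with the exclusion: "Symptoms of CHB will not be reported as adverse events". The protocol nowhere says which symptoms these are, whether they must have been present before dosing, or who decides.

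Section 13.2 has subjects questioned about adverse events at every return visit and requires all events to be entered in the subjects' "medical records and in the EDC system". Section 13.1 has the investigator answer a yes/no causality question for each adverse event, assuming under blinding that every subject takes the test drug.

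Section 4.2.2.1 lists the common events on the extended release tablets: diarrhea 6.4%, chromaturia 4.7%, headache 3.5%, nausea 3.1%, abdominal pain 3%, bronchitis 2.7% and vomiting 2.3%. For long-term use it adds "Mild and transient yellow discoloration of the urine and sclera". The instructions to subjects in Section 9.2 ask them to call about stomach pain, nausea and vomiting, brown or dark urine, and "Yellowing of eyes or sclera".

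Safety is a study objective (Section 5). Section 11.1 describes the purpose as evaluating safety and efficacy against placebo in order to select a dose. Section 11.4.2 makes the safety analysis descriptive.

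**The concern.** The exclusion asks for a judgement of cause before an event is recorded. A symptom judged to be CHB never becomes an adverse event. It therefore never meets the causality question in Section 13.1, and the instruction to assume that every subject is on the test drug cannot protect it. It is also absent from the safety tables.

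The symptoms most open to this judgement in a liver disease resemble what the protocol reports for nitazoxanide. This matters for the purpose of the trial: the dose rationale in Section 6 sets the top dose by reference to gastrointestinal effects seen at higher doses, so non-serious gastrointestinal symptoms bear on the choice between regimens. Section 16 states that there is no independent data monitoring committee, so the recorded events are the main basis for judging tolerability.

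The exclusion also gains little. No efficacy endpoint is symptom-based, and the placebo arm already shows the background rate of CHB symptoms.

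**Working it through.** The protocol gives no figure for adverse event counts that could be reproduced. Its only design calculation (Section 11.1) concerns the primary efficacy t-test and does not bear on this point.

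**Step 1. The texts side by side.**
- Section 13, definition: any unwanted change after the first dose, whatever its relation to the study.
- Section 13, exclusion: symptoms of CHB are not reported.
- Section 13.2: all events are recorded.

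A post-dose symptom attributed to CHB meets the first and third rules and is barred by the second. No passage says which prevails.

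**Step 2. Overlapping terms.** The protocol has no list of CHB symptoms, so the overlap is inferred from Sections 4.2.2.1 and 9.2. The terms common to both are chromaturia, nausea, abdominal pain and vomiting. Diarrhea, headache and bronchitis are left out. Yellow sclera overlaps too, but no rate is given for it.

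Sum of rates: 4.7% + 3.1% + 3.0% + 2.3% = 13.1%. This is a sum of event rates, not a proportion of subjects.

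**Step 3. Expected events if all are recorded.**
- Per arm: 12 × 0.131 = 1.57.
- All nitazoxanide subjects: 36 × 0.131 = 4.72.

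**Step 4. Events lost.** Let q be the share set aside as CHB. The documents give no value, so a range is assumed.

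| q | Lost per 12-subject arm (1.57 × q) | Lost in 36 nitazoxanide subjects (4.72 × q) |
|---|---|---|
| 10% | 0.16 | 0.47 |
| 25% | 0.39 | 1.18 |
| 50% | 0.79 | 2.36 |

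**Step 5. Effect on a comparison with placebo.** If q is the same in all blinded arms, each recorded rate is p × (1 − q). The difference shrinks by the factor (1 − q) and the ratio is unchanged. Chromaturia, the one event that Section 4.2.2.1 reports as differing from placebo (4.7% against 0.2%), illustrates this:
- q = 0: difference 4.5 points, ratio 4.7/0.2 = 23.5.
- q = 10%: 4.5 × 0.90 = 4.05 points, ratio 23.5.
- q = 25%: 4.5 × 0.75 = 3.4 points, ratio 23.5.
- q = 50%: 4.5 × 0.50 = 2.25 points, ratio 23.5.

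**Limits of the inputs.** Of the 1,760 subjects behind these rates, 1,374 (78%) received 600 mg twice daily for 5 days. The rates are only a rough guide to 12 weeks or more of treatment.

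**The case against.** The strongest reply is that the rule would rarely bite and that other data catch much of what it removes.

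- **Population.** Subjects have been suppressed for at least 12 months with ALT below 1.5 times the upper limit (Section 7.1), and cirrhosis and decompensation are excluded (Section 7.2). An investigator who expects few CHB symptoms has little reason to blame CHB for new nausea. This stands as a reason to expect a small q. It equally shows how little the exclusion is needed.
- **Other routes.** Unexpected worsening and significant laboratory changes remain adverse events, and serious events must be reported whatever their cause (Sections 13.2 and 13.3). Urinalysis, including appearance, and liver tests are done at every on-treatment visit except Day 3 (Section 9.3). These cover flares, serious events and part of chromaturia. They do not cover non-serious nausea, vomiting or abdominal pain.
- **Section 13.2.** Its all-events wording could be read as covering only what already counts as an adverse event. On that reading the conflict with Section 13.2 falls away, but the one inside Section 13 remains.
- **Descriptive analysis.** No test depends on these counts. That is so, but absolute rates are then what the reader is shown, and those are what the exclusion lowers.

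A reader might infer stronger claims that the documents do not support:

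- **That the exclusion removes only drug signal.** It is applied blind in every arm and also removes background events.
- **That each unreported subject costs 8.3 percentage points.** This is 1/12 and holds for any subject in any arm. It changes an arm's overall adverse event rate only if the excluded symptom was that subject's sole event.
- **That the Section 14 rule is materially weakened.** More than 20% of 48 subjects means at least 10 (0.20 × 48 = 9.6), each with a drug-related Grade 3 or 4 event. Section 4.2.2.1 describes the long-term gastrointestinal events as mild to moderate. An investigator who attributes a symptom to CHB would probably also answer no on causality. Any figure for this effect needs a Grade 3–4 rate that the documents do not give.
- **That Section 9.6 contradicts the exclusion** by listing "Clinical signs of hepatic decompensation" among adverse events requiring discontinuation. That entry concerns signs of worsening disease, so it narrows the exclusion.

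**Conclusion.** The point holds as an internal conflict in the safety reporting rules that can, but need not, reduce the recorded counts. Non-serious post-dose symptoms resembling known nitazoxanide effects can be kept out of the tables without a causality assessment.

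On the figures available the expected loss is below one event per arm, even if half of the overlapping events were set aside. With 12 subjects per arm and about 1.6 such events expected in each, that could still alter how the regimens look beside one another.

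The estimate rests on three assumptions: the inferred list of overlapping terms, rates carried over mostly from 5-day dosing, and an assumed q of 10% to 50%. The statement that ratios are preserved needs q to be equal across arms. To say that the plan *will* under-count would go beyond the documents, because nothing in them fixes how often investigators would use the exclusion.

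**What to change.** Delete the sentence in Section 13 that excludes CHB symptoms. State that every untoward event after the first dose is recorded whatever its suspected cause, and leave attribution to the causality question already in Section 13.1. Add one field to the adverse event form for suspected attribution to CHB, so that the safety tables can be shown by arm with and without those events. Section 13.2 then needs no change.

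The cost is one protocol sentence, one data field and a few more adverse event records. Reported rates would rise slightly in all arms, including placebo.
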